2.1. Associate Investigators (AI): See attached A2 Study Personnel Form

2.2. Research Assistants (RA) & Coordinators (RC): See attached A2 Study Personnel Form

2.3. The research relevance of this protocol focuses on:

Diagnosis Treatment Medical Utilization/Managed Care Prevention Medical Readiness Other

2.4. Location(s):

a. Collaborating Facilities: None.

b. Air Force Sites seeking Regional IRB:

Air Force Sites	Name	Email	Phone
Nellis Air Force Base	[name], MBA/HCM, CCRP, CCRC	[contact]	[contact]

c. List study sponsors: Integrity Nutraceuticals, Inc. and AFMSA/SG9S

3. Research Plan:

3.1. Purpose:

The purpose of this study is to assess whether water-soluble cinnamon extract plus aggressive lifestyle intervention is effective in lowering blood glucose in pre-diabetic patients when compared to aggressive lifestyle therapy plus placebo.

3.2. Hypotheses, Research Questions or Objectives:

Does water-soluble cinnamon extract have an effect on fasting glucose, Hemoglobin A1c, lipid panel, and waist circumference in pre-diabetic patients who are already undergoing aggressive lifestyle therapy?

This study has the following goals:

1. Determine the length of time to diagnosis of diabetes using any of the ADA criteria.
2. Determine:
 - a) Fasting glucose
 - b) Hemoglobin A1C
 - c) LDL cholesterol, and
 - d) Waist circumference (in inches)

3.3. Significance:

Lowering hemoglobin A1c is correlated with reduced complications in Type 2 diabetes (e.g., retinopathy, nephropathy, neuropathy, vascular disease, and death). Water-soluble cinnamon extract is inexpensive, readily available, generally recognized as safe, and a non-pharmacological approach to management. According to the 2010 American Diabetes Association Guidelines, lifestyle intervention is the most effective way for diabetes. Historically, it has been difficult for subjects to adhere to lifestyle education programs and sustain meaningful weight loss without using significant resources, as in the Diabetes Prevention Study (NEJM, 2002).

3.4. Military Relevance:

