Cinnamon may improve glycemic control and insulin sensitivity.⁹ To date, seven randomized trials studying cinnamon in humans with Type 2 diabetes have been published with conflicting results.¹⁰⁻¹⁵ The results of these studies are mixed. Two of these studies showed a possible effect of cinnamon on fasting serum glucose, but they did not examine hemoglobin A1c levels.^{10,11} One study showed no effect on plasma glucose.¹² Two studies--one each in patients with Type 1 and Type 2 diabetes--showed no effect of cinnamon on Hemoglobin A1c.^{13,14} Cinnulin PF® supplementation reduced fasting blood glucose and systolic blood pressure, and increased lean body mass in a randomized trial in men and women with the metabolic syndrome.¹⁶ A meta-analysis of these studies in divergent populations measuring different parameters showed no effect of cinnamon on hemoglobin A1c, glucose or lipids.¹⁷ Subsequently, a RCT of 109 patients compared add-on treatment with 1 gram daily of cinnamon over a 3 month period to usual care in a population of poorly controlled Type 2 diabetics, it found that cinnamon lowered hemoglobin A1c 0.83%--similar to some prescription drugs.¹⁵ This led to a call for more comparative effectiveness research of cinnamon versus prescription medications.¹⁸

There have been no trials assessing if water-soluble cinnamon extract is effective at lowering blood glucose. Guidelines recommend that new diabetics receive treatment with Metformin to help with insulin sensitization, lower blood glucose, and assist with weight loss. Water-soluble cinnamon extract appears to have many of the same mechanisms of Metformin.

Research has shown that pre-diabetics convert to diabetes at an average of 7% a year and other research performed on prevention have been multi-year trials. In order to obtain adequate power for this study, subjects will take water-soluble cinnamon extract or placebo for 1 year.

3.5.1. Bibliography:

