 - o Fasting comprehensive metabolic panel (liver function, renal function, plasma glucose tests) via 1 venipuncture (5-10 mls, approximately 1-2 teaspoons of blood will be drawn)
**Subjects who have had a fasting comprehensive metabolic panel test within the two weeks prior to Visit 1 will not need to have this test repeated.*
 - o Hemoglobin A1c via 1 venipuncture (5-10 mls, approximately 1-2 teaspoons of blood will be drawn)
**Subjects who have had a Hemoglobin A1c test within the two weeks prior to Visit 1 will not need to have this test repeated.*
 - o Lipid panel via 1 venipuncture (5-10 mls, approximately 1-2 teaspoons of blood will be drawn)
**Subjects who have had a lipid panel within the two weeks prior to Visit 1 will not need to have this test repeated.*

Visit 1 (Day 1 within-30 days of Screening Visit*labs must be re-done if greater than 2 weeks from Screening Visit):

- Record: whether subject is taking any statins, fibrates, niacin or bile acid binding agent and, if yes, the name of drug, strength and dose.
- Subjects will complete the RAND 36 Item Health Survey.
- Subjects will be randomized by a non-investigator at the pharmacy. We will use a random-number generator and use blocking to ensure roughly equal sample sizes. Both subjects and investigators will be blinded to the study group assignments. Subjects will be randomized by the pharmacy into one of two groups (research-driven):
 - o Group 1: Will take (by mouth) 2 gelatin capsules that contains 1 gram (2-500 mg capsules) water-soluble cinnamon extract (Cinnulin PF) once a day for 1 year plus 2 years of follow-up plus standard of care aggressive lifestyle therapy.
 - o Group 2: Will take (by mouth) 2 placebo capsules (gelatin capsule filled with wheat bran) once a day for 1 year plus 2 years of follow-up plus standard of care aggressive lifestyle therapy.

- Subjects will be provided a pill container to assist with remembering to take their IP and a bathroom scale to weigh themselves with (if available).
- Subjects will be given a Study Medication Diary and will be instructed to bring it with them to next study visit.
- Subjects will be told to fast for at least 10 hours prior to Visit 2.

Visit 2-Month 3 (90 days after Visit 1):

- Record: Weight (in pounds), waist circumference (in inches), blood pressure, verify current email address , and whether subject is taking any statins, fibrates, niacin or bile acid binding agent and, if yes, the name of drug, strength and dose.

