**Subjects who have had a fasting comprehensive metabolic panel test within the two weeks prior to Visit 3 will not need to have this test repeated.*
 - o Hemoglobin A1c via 1 venipuncture (5-10 mls, approximately 1-2 teaspoons of blood will be drawn).
**Subjects who have had a Hemoglobin A1c test within the two weeks prior to Visit 3 will not need to have this test repeated.*
 - o Lipid panel via 1 venipuncture (5-10 mls, approximately 1-2 teaspoons of blood will be drawn).
**Subjects who have had a lipid panel within the two weeks prior to Visit 3 will not need to have this test repeated.*

Visit 4-Month 9 (90 days after Visit 3):

- Record weight (in pounds), waist circumference) (in inches), blood pressure, verify current email address , and whether subject is taking any statins, fibrates, niacin or bile acid binding agent and, if yes, the name of drug, strength and dose.
- Study staff will also record whether subjects had any side effects to report to include cardiovascular procedures and events and other morbidity data (research-driven).
- Subjects will bring in any remaining medication to determine adherence rates to the study protocol.
- Research staff will collect the subject's Study Medication Diary and issue them a new one.
- Subjects will be told to fast for at least 10 hours prior to Visit 5.
- Refill water-soluble cinnamon extract or placebo (research-driven).
- Subjects will have standard of care blood test drawn to include:
 - o Fasting comprehensive metabolic panel (liver function tests, renal function, and plasma glucose test) via 1 venipuncture (5-10 mls, approximately 1-2 teaspoons of blood will be drawn).
**Subjects who have had a fasting comprehensive metabolic panel test within the two weeks prior to Visit 4 will not need to have this test repeated.*

- o Hemoglobin A1c via 1 venipuncture (5-10 mls, approximately 1-2 teaspoons of blood will be drawn)
**Subjects who have had a Hemoglobin A1c test within the two weeks prior to Visit 4 will not need to have this test repeated.*
- o Lipid panel via 1 venipuncture (5-10 mls, approximately 1-2 teaspoons of blood will be drawn)
**Subjects who have had a lipid panel within the two weeks prior to Visit 4 will not need to have this test repeated.*

Visit 5-Month 12 (90 days after Visit 4) *SUBJECTS STOP TAKING STUDY MEDICATIONS AT THIS VISIT:

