**Subjects who have had a fasting glucose test within the two weeks prior to Visit 8 will not need to have this test repeated.*
 - o Hemoglobin A1c via 1 venipuncture (5-10 mls, approximately 1-2 teaspoons of blood will be drawn).
**Subjects who have had a hemoglobin A1c test within the two weeks prior to Visit 8 will not need to have this test repeated.*
 - o Lipid panel via 1 venipuncture (5-10 mls, approximately 1-2 teaspoons of blood will be drawn).
**Subjects who have had a lipid panel within the two weeks prior to Visit 8 will not need to have this test repeated.*

Visit 9-Month 24 (90 days after Visit 8):

- Record: Weight (in pounds), waist circumference (in inches), blood pressure, verify current email address , and whether subject is taking any statins, fibrates, niacin or bile acid binding agent and, if yes, the name of drug, strength and dose.
- Subjects will complete the RAND 36 Item Health Survey.
- Study staff will also record whether subjects had any side effects to report to include cardiovascular procedures and events and other morbidity data (research-driven).
- Subjects will have research-driven blood tests drawn which include:
 - o Fasting plasma glucose via 1 venipuncture (5-10 mls, approximately 1-2 teaspoons of blood will be drawn).
**Subjects who have had a fasting glucose test within the two weeks prior to Visit 9 will not need to have this test repeated.*
 - o Hemoglobin A1c via 1 venipuncture (5-10 mls, approximately 1-2 teaspoons of blood will be drawn).
**Subjects who have had a Hemoglobin A1c test within the two weeks prior to Visit 9 will not need to have this test repeated.*
 - o Lipid panel via 1 venipuncture (5-10 mls, approximately 1-2 teaspoons of blood will be drawn).
**Subjects who have had a lipid panel within the two weeks prior to Visit 9 will not need to have this test repeated.*

VISIT WINDOWS: Visits have a window of plus or minus 10 days. Subjects are encouraged to come in as close to the 90 day mark as possible since they are only given a 90 day supply of IP. Postponement of any follow up visits (after subject stopped taking study medication) is authorized for up to 6 weeks in case of a temporary condition that would affect glucose tolerance (i.e. moderate to severe illness to be determined by study PI or Site AI). A note to file documenting such shall be placed in the subject's study folder and documented in the data collection form.

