3.6.4. Date(s): April 2012-April 2018

3.6.5. Source of Research Material:

Source of Research Material per Participant (Procedures)	# Routine Care	# Research Driven	# Total Procedures
Group 1 Only: 1 gram (2-500 mg capsules) water-soluble cinnamon extract (Cinnulin PF) (once a day for 1 year)	0	1 year	1 year
Group 2 Only: 2 placebo pills (once a day for 1 year)	0	1 year	1 year
Fasting glucose	0	3	3
Fasting comprehensive metabolic panel	3	3	6
Hemoglobin A1C	4	5	9
ECG	0	2	2
Lipid panel	4	5	9
Study Medication Diary	0	4	4
RAND 36-Item Health Questionnaire	0	3	3

"All specimens collected at Nellis AFB will be kept at Nellis AFB and handled and disposed of in accordance with federal regulations."

3.6.6. Subjects:

We will recruit male and female subjects Nellis AFB between the ages of 18-65 years with a diagnosis of pre-diabetes. Eligible subjects will be recruited from any form and any stage of "standard" lifestyle intervention for pre-diabetes at an individual base. "Standard" lifestyle intervention for pre-diabetes could include Group Lifestyle Balance (GLB), nutrition classes, Better Body/Better Life, or anything an investigator certifies as standard practice at that base. No special populations (i.e. children, prisoners, pregnant women, mentally disabled persons, or economically or educationally disadvantaged persons) will be eligible for this study. There are currently 2,950 diabetic patients empaneled for care at Nellis AFB. Several thousand more are pre-diabetic--many of these will likely attain the diagnosis of diabetes within 36 months.

3.6.7. Inclusion/Exclusion Criteria:

Inclusion:

- Patients will be Nellis AFB DoD beneficiaries between the ages of 18-65 years.
- Diagnosis of pre-diabetes (defined as a fasting plasma glucose (FPG) 100-125mg/dl or hemoglobin A1C 5.7-6.4% or a 2-hour oral glucose tolerance test (OGTT) 140-199).

Exclusion:

- Patients who are less than 18 yrs of age or greater than 65 years of age
- Patients who are known to have or develop during the study any of the following upon review of their medical record:
 - o Diabetes Mellitus (defined as fasting plasma glucose (FPG) ≥126mg/dl, hemoglobin A1C ≥6.5%, or a 2-hour oral glucose tolerance test (OGTT) ≥200mg/dl)

- o Stage 3 kidney disease or worse
- o Renal insufficiency defined as a glomerular filtration rate (gfr) of less than 60ml
- o Celiac disease
- o Insulinoma
- o Cushing's disease
- o Hyperthyroidism
- o Acromegaly
- o Pheochromocytoma
- o Addison's disease

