6.2. Sample size estimation/power analysis:

A priori power for H₀₁ was assessed using G*Power Version 3.0.10¹. The results indicate 214 subjects per group with 8 repeated measures for a total sample size of 3424 will achieve a power of approximately 0.99 to detect a small effect size of 0.10 at α = 0.0004.

A priori power for H₀₂ was assessed using the method described by Glantz² to calculate sample size for a two-sample log-rank test to detect differences in the time to event. Based on this design, it will require a minimum of 214 subjects per group to detect a difference between a 17.5% conversion in the Placebo + lifestyle and an 11.5% conversion in the Cinnulin + lifestyle group at α = 0.05 (one-sided) and power of 0.80.

We are enrolling 557 subjects total, for an expected 428 completing the study. We estimate 129 subjects' will either withdraw consent or drop out of the study.

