A priori power for H_02 was assessed using the method described by Glantz⁵ to calculate sample size for a two-sample log-rank test to detect differences in the time to event. Based on this design, it will require a minimum of 214 subjects per group to detect a difference between a 17.5% conversion in the placebo + lifestyle and an 11.5% conversion in the cinnulin + lifestyle group at $\alpha = 0.05$ (one-sided) and power of 0.80.

Power Analysis Log-Rank Test for Two Samples	
α	0.050
$Z_{.05(2)}$	1.64
$1-\beta$	0.80
$Z_{.80(\text{upper})}$	-0.842
$S_2(\infty)$	0.885
$\text{Ln}S_2(\infty)$	-0.122168
$S_1(\infty)$	0.825
$\text{Ln}S_1(\infty)$	-0.192372
ψ	0.6350597
d (primary endpoint events) =	124
n (sample size to achieve this number of events) =	428
Groups/Treatments	2
Subjects required per group/treatment	214

Steps of Analysis

Descriptive statistics: Sample means and standard errors of measurement of interval variables will be calculated, and frequency distributions of nominal variables will be calculated and graphed for the total sample and for the Cinnulin/Lifestyle Management groups. Homogeneity of the groups will be tested with a two-tailed *t*-test and two-tailed Fisher's exact test for interval and nominal variables respectively.

Hypothesis Testing

H_01 – This hypothesis will be tested by a mixed effects repeated measures analysis of variance (rANOVA).

H_02 – This hypothesis will be tested by developing Kaplan-Meier survival curves and survival functions compared with a log-rank test.

Post Hoc Tests: In the event H_01 is rejected, contrasts will be used to investigate effects and differences within clinically significant time intervals. In the event multiple univariate tests are used to investigate effects, the Bonferroni⁶ or Holm's method⁷ will be used to correct the level of significance for multiple comparisons.

Analysis Tools:

SAS Version 9.2 for Windows (SAS Institute, Cary, North Carolina)

R Version 2.13.1 (R Foundation for Statistical Computing)

Microsoft Excel (Microsoft Corporation, Seattle, Washington)

6.4 Number of Subjects:

Number of subjects recruited at WHASC	46
---------------------------------------	----

⁵ Glantz SA. *Primer of Biostatistics*. McGraw-Hill, 2002, 438-440.

⁶ Abdi H. Bonferroni and Šidák. Corrections for multiple comparisons. In N.J. Salkind (ed.). *Encyclopedia of Measurement and Statistics*. 2007; Thousand Oaks, CA: Sage.

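### At 214 per group the log-rank test for time to diabetes has power of about 0.55, not 0.80, and the two conversion rates behind it have no time point or source

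*Combined protocol and SAP*

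**What the plan says.** Protocol section 6.2 and the H02 power table in the SAP (section 6.3) plan to detect "17.5% conversion in the placebo + lifestyle and an 11.5% conversion in the cinnulin + lifestyle group" with a one-sided log-rank test at 0.05 and power 0.80. The table lists 124 events, a sample size of 428 to obtain them, two groups, and 214 per group. It writes the two survival proportions as values at infinity, 0.825 and 0.885, and gives neither a month nor a reference for them.

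Section 6.2 adds: "We are enrolling 557 subjects total, for an expected 428 completing the study".

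On conversion, section 3.5 says that "pre-diabetics convert to diabetes at an average of 7% a year". Section 3.6.6 says of pre-diabetic patients at the site that "many of these will likely attain the diagnosis of diabetes within 36 months", with no rate. The research question in section 3.2 concerns "pre-diabetic patients who are already undergoing aggressive lifestyle therapy".

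On timing, the Visit 5 (Month 12) heading in section 3.6 states "SUBJECTS STOP TAKING STUDY MEDICATIONS AT THIS VISIT", and the last entry in the visit list is "Visit 9-Month 24 (90 days after Visit 8").

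**The concern.** Log-rank power depends on the number of events observed. Two things in the H02 calculation affect that number.

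First, the table goes from 124 events to 428 subjects and then halves 428 to get the group size. If 428 is already a per-group figure, the trial is half the size that its stated power requires.

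Second, a cumulative conversion of 17.5% means little without a time point. Visits stop at Month 24, and the one annual rate in the documents does not reach 17.5% by then.

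Time to diagnosis of diabetes is the first goal listed in section 3.2. A reader who trusts power of 0.80 would take a null log-rank result as fair evidence against a 37% hazard reduction, when the test would miss that effect about half the time.

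**Working it through.** **Inputs.** From the SAP table: S1 = 0.825, S2 = 0.885, one-sided 0.05, power 0.80, 214 per group. From section 3.5: 7% a year. From the visit list: last visit at Month 24, product stopped at Month 12. From section 6.2: 557 enrolled, 428 completing, 129 lost.

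**1. The plan's event count reproduces.**
- Hazard ratio = ln(0.885)/ln(0.825) = 0.635.
- (1 − 0.635)/(1 + 0.635) = 0.2232.
- Events (Freedman) = (1.64 + 0.842)² / 0.2232² = 123.7, so 124.

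**2. The group size does not.**
- Events expected with n per group = n × (0.175 + 0.115) = 0.29n.
- n = 124/0.29 = 427.6, so 428 per group, or about 855 in total.
- A one-sided two-proportion calculation gives 425 per group, so the finding does not depend on the formula.

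**3. Power at 214 per group and the stated rates.**
- Events = 214 × 0.29 = 62.1.
- Power = Φ(√62.1 × 0.2232 − 1.645) = 0.545. Schoenfeld's formula gives 0.557 and two proportions 0.547.

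**4. What 7% a year gives by Month 24**, with the hazard ratio held at 0.635 throughout:
- Placebo: 1 − 0.93² = 13.5%. Active: 1 − 0.8649^0.635 = 8.8%.
- Events = 214 × (0.1351 + 0.0881) = 47.8; power = 0.459.
- Reading 7% as a hazard (13.1% placebo) gives 46.2 events and 0.449; reading it as linear (14.0%) gives 49.5 and 0.470.
- 17.5% by Month 24 needs 1 − √0.825 = 9.2% a year. At 7% it is reached after 2.5 years (linear) or 2.65 years (compounded).

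**5. Month 24 power by annual placebo rate**, 214 completers per group:

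| Annual rate | Placebo | Active | Events | Power |
|---|---|---|---|---|
| 5% | 9.8% | 6.3% | 34 | 0.37 |
| 6% | 11.6% | 7.6% | 41 | 0.42 |
| 7% | 13.5% | 8.8% | 48 | 0.46 |
| 8% | 15.4% | 10.1% | 54 | 0.50 |
| 9.2% | 17.5% | 11.5% | 62 | 0.55 |

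**6. Counting all 557 randomised.** Dropouts contribute events until they leave. If the 129 leave uniformly over 24 months (an assumption), 7% a year gives about 55 events and power 0.50, and 9.2% gives about 72 and 0.60. With no dropout at all, the ceiling is about 0.55 and 0.64.

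**7. If the effect ends with the product.** At 7% a year and 214 per group, about 24.6 events fall in year 1 (hazard ratio 0.635) and 28.2 in year 2 (hazard ratio 1). Power = Φ(24.6 × 0.2232/√52.9 − 1.645) = 0.19.

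**8. Separating the two issues.** The halving takes power from 0.80 to 0.55 at the stated rates. Using 7% a year then takes it from 0.55 to 0.46. With 428 per group, 7% a year would give 95.5 events and power 0.70.

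**The case against.** The best defence concerns the rates. The 7% is a background average for pre-diabetics in general, carries no citation where it appears, and is not offered as the power input. Lifestyle therapy in both arms could lower the rate, and quarterly testing against any ADA criterion could raise it. So the comparison sets one unsourced figure against another and does not prove 17.5% wrong. That stands: 7% is one point in a range.

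It is also fair that 214 per group counts completers only, while the plan follows intention-to-treat principles. Events among dropouts add power. That stands too, but even the no-dropout ceiling of 0.64 at the stated rates is short of 0.80. Subjects who stop and restart product resume at their last documented visit, so a few may be observed beyond 24 calendar months; the documents give no number.

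A reader might make three stronger inferences that the documents do not support:
- That the missing time point explains the whole shortfall from 0.80. Most of it comes from the halving.
- That 17.5% was derived as 7% over 2.5 years, or for a 36-month design. The Visit 1 arm descriptions say "once a day for 1 year plus 2 years of follow-up", but sections 3.6.1 and 4 of the summary say one year of follow-up, and no visit after Month 24 is listed. No passage links either horizon to the power table, so the arm wording is best treated as clerical. Nor does any passage say that the rates refer to Month 24.
- That 0.19 is a lower bound. It assumes full effect from day 1, an abrupt end at Month 12, and 7% a year; a lower rate or a delayed onset would give less.

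**Conclusion.** The stated power of 0.80 for H02 is not delivered by 214 per group. On the plan's own rates, hazard ratio and one-sided 0.05, it is about 0.55, with about 62 of the 124 required events. This part needs no outside assumption beyond complete follow-up of 428 subjects.

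The missing time point and source is a separate, smaller and conditional weakness. If placebo conversion runs near 7% a year and the hazard ratio holds for all 24 months, power is about 0.46. The rates are unsupported and high against the one figure given; they are not shown to be wrong.

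**What to change.** In sections 6.2 and 6.3:
- Replace the stated power of 0.80 with about 0.55 at the stated rates for 214 per group, and correct the table so that 428 is shown as the per-group number for 124 events.
- State the time point and the source of the 17.5% and 11.5%. The authors should supply the time point they actually used; Month 24 should not be presumed.
- State whether the hazard ratio is assumed to hold after product stops at Month 12.
- Add the Month 24 sensitivity table for 214 completers per group (step 5), with the figures for all 557 randomised: about 0.50 at 7% and 0.60 at 9.2% under uniform dropout, with a ceiling of 0.55 and 0.64. Show the case where the effect ends at Month 12 (about 0.19 at 7% a year) as a scenario.

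As an editorial matter, bring the follow-up length in the two Visit 1 arm descriptions into line with the visit list.

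The cost is wording, one short table, and an openly lower stated power. Enrolment, visits, data and the log-rank test do not change.

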6.3. Statistical Analysis: Statistical Analysis Plan

Protocol	Assessment of the effect of lifestyle intervention plus water-soluble cinnamon extract on lowering blood glucose in pre-diabetics: A randomized, double-blind, multicenter, placebo controlled TRIAL.
Principal Investigator(s)	Lt Col [name], USAF, MC 99 th MDG
Statistical Analysis Plan	[name], Ctr AFMSA/SG5M South
Statistical Analysis	[name], Ctr AFMSA/SG5M South

Technical Objective: The objective of this study is to compare Cinnulin PF, a cinnamon extract, in combination with a lifestyle management program, to a placebo and life style management program, and to evaluate the prevention or delay the development of Type 2 diabetes in persons with pre-diabetes.

Sample: Subjects will be a random sample of males and females between the ages of 18-65 years with a diagnosis of pre-diabetes seen in certain Air Force medical treatment facilities. The subjects are presumed to be randomly selected from the population of patients obtaining similar care at all Air Force medical treatment facilities.

Hypothesis:

H₀₁ – No difference in means of continuous dependent variables between and among treatment groups
H₀₂ – Cinnulin + Life Style and Placebo + Life Style groups have identical survival functions for the time to reach the Type 2 diabetes conversion event.

Study Design: The experimental design of this study is a mixed effects, randomized complete block design with repeated measures. Subject is a random effect as the subjects are a sample randomly selected and randomly assigned to a treatment group. Fixed effects are treatment group and time of repeated measure as these effects cannot be generalized to other treatments and times. Subjects will be randomly assigned to each treatment group.

Factors:

1. Subject
2. Treatment: Cinnulin PF + Life Style Management versus Placebo + Lifestyle Management
3. Repeated Measurements: Laboratory and physical measurements obtained from each subject at fixed intervals for the duration of the study (N=8).

¹ Faul F, Erdfelder E, Lang A-G, Buchner A. G*Power 3: A flexible statistical power analysis program for the social, behavioral, and biomedical sciences. *Behavior Research Methods*. 2007; 39 (2): 175-191.

² Glantz SA. *Primer of Biostatistics*. McGraw-Hill, 2002, 438-440.

Outcome Variables:

1. Diabetic indicators
 - a. Glucose
 - b. Hemoglobin A1c
 - c. Lipid panel (cholesterol, triglycerides, HDL, LDL)
 - d. Waist circumference

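### The log-rank test of H02 is valid, but it leaves baseline fasting glucose and HbA1c unused, and the SAP names no effect measure or interval, so the size of any delay in diabetes is not quantified

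*Combined protocol and SAP*

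**What the plan says.** Goal 1 in section 3.2 is: "Determine the length of time to diagnosis of diabetes using any of the ADA criteria". The SAP (section 6.3) turns this into H02, the null that the two "groups have identical survival functions for the time to reach the Type 2 diabetes conversion event". The whole analysis of H02 is one sentence: "This hypothesis will be tested by developing Kaplan-Meier survival curves and survival functions compared with a log-rank test". Nothing in section 6.3 gives a hazard ratio, a confidence interval, a covariate or a summary on the time scale for this endpoint.

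The power text for H02 is built on a "17.5% conversion in the placebo + lifestyle and an 11.5% conversion in the cinnulin + lifestyle group", with one-sided α of 0.05 and power of 0.80. Its table attaches no calendar time to the two survival values.

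The baseline data exist. Section 3.6 obtains a fasting metabolic panel (which includes plasma glucose) and HbA1c at screening, accepts results from the two weeks before Visit 1, and has the labs repeated if they are older than that. Sections 3.6.7 and 6 of the summary admit a subject on any one of three criteria: fasting glucose 100–125 mg/dl, HbA1c 5.7–6.4%, or a 2-hour OGTT of 140–199. They define diabetes by 126 mg/dl, 6.5% or 200 mg/dl on the same three tests. Section 6.3 tests the groups for homogeneity at baseline and lists demographic variables of interest, but puts neither these nor the baseline labs into a model for H02.

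**The concern.** The event is the later crossing of a threshold on measures that are already known at entry. A subject entering at a fasting glucose of 124 has much less far to go than one entering at 101. Because the entry criteria are joined by an or, some subjects will enter with one of the measures in the normal range. Some prognostic value therefore follows from the design, and an unadjusted test does not use it.

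Goal 1 asks how long it takes to reach the diagnosis, and the SAP's technical objective speaks of prevention or delay. Both ask about amount. A log-rank p-value says only whether the curves differ. Without an interval, a non-significant result would be easily read as no effect, even where the data could not exclude a large reduction.

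**Working it through.** **Inputs from the documents.** Diabetes-free proportions 0.825 and 0.885; one-sided α 0.05; 214 per group; visits every 3 months, ending at Month 24.

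**Assumptions.** (a) The 17.5% and 11.5% rates apply at 24 months. (b) Baseline glycaemia acts as one normally distributed risk score whose log-hazard SD lies between 0.5 and 1.5. Neither is in the documents.

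**1. The plan's own figures.** Hazard ratio ψ = ln 0.885 / ln 0.825 = −0.122168 / −0.192372 = 0.635. Events d = (1.64 + 0.842)² × [(1 + 0.635)/(1 − 0.635)]² = 123.7 with unrounded ψ, which matches the stated 124. Then 124 / (2 − 0.825 − 0.885) = 427.6. This is the number per group, but the SAP uses 428 as the total. That is a separate sample-size problem. It matters here because it sets the events actually expected: 214 × (0.175 + 0.115) = 62.

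**2. Unadjusted power at 62 events.** Expected z = √(62.06/4) × |ln 0.635| = 3.94 × 0.454 = 1.79. Power = Φ(1.79 − 1.645) ≈ 0.56.

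**3. What adjustment adds.** Simulated trials, 2000 per setting: 214 per arm, exponential times, marginal 24-month risks held at 17.5% and 11.5%, events moved to the next 3-monthly visit, Cox model with Breslow ties. The information ratio is (mean adjusted z / mean unadjusted z)².

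| Log-hazard SD (assumed) | Power, unadjusted | Power, adjusted | Information ratio |
|---|---|---|---|
| 0.5 | 0.51 | 0.54 | 1.05 |
| 0.7 | 0.56 | 0.59 | 1.08 |
| 1.0 | 0.57 | 0.63 | 1.17 |
| 1.5 | 0.53 | 0.69 | 1.48 |

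The 0.5 row comes from a separate run of the same design. The Monte Carlo standard error of one power figure is √(0.55 × 0.45 / 2000) = 0.011, so the gain within a row says more than the differences between rows. A run with exact event times (4000 trials per setting) gave 0.55 to 0.56 at SD 0.5, 0.55 to 0.61 at SD 1.0, and 0.56 to 0.72 at SD 1.5. The low end of the gain may thus be nearer 1 point than 3. Only at an extreme SD of 2.0 (hazard ratio 7.4 per SD) did adjusted power reach 0.82.

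**4. Time scale.** With 82.5% and 88.5% still diabetes-free, neither curve reaches 50%, so there is no median to report. Restricted mean diabetes-free time to 24 months is p/λ with λ = −ln(1 − p)/24:
- placebo: 0.175 / 0.008016 = 21.83 months
- cinnamon: 0.115 / 0.005090 = 22.59 months
- difference: 0.76 month at the planned effect

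If the planned rates applied at 36 months instead, the 24-month difference would be 0.52 month.

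**5. The missing interval.** At 62 events the standard error of the log hazard ratio is √(4/62) = 0.254. An observed hazard ratio of 0.635 has a 95% interval of 0.635 ÷ and × exp(1.96 × 0.254), or 0.39 to 1.04. The matching 90% interval is 0.635 ÷ and × exp(1.645 × 0.254), or 0.42 to 0.96. The same result would therefore pass the one-sided 0.05 test while its 95% interval includes 1, so the level of the reported interval has to be settled in advance.

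**The case against.** The log-rank test addresses the null as H02 states it, is the test for which the sample size was derived, and needs no covariate model in a randomised trial. That stands: the choice is a missed improvement and not an error.

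A reader might infer that the plan yields no time estimate and leaves goal 1 unanswered. The documents do not support that. The planned Kaplan-Meier curves estimate the diabetes-free proportion over time in each arm. What is missing is a between-arm measure with an interval.

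The size of the power gain rests on a prognostic strength that the documents do not give. Up to a log-hazard SD of 1.0 the gain is modest, and a single linear score is a simplification of three entry criteria joined by an or. The 24-month horizon is also assumed. The SAP's survival values carry no time, and the protocol gives follow-up after the treatment year as one year in section 3.6.1 and as two years in the group descriptions at Visit 1, which must be reconciled. These points stand, and the figures are given as ranges for that reason.

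A reader might also blame the log-rank test for the wide interval and the low power. Both come from having 62 events rather than 124. At 124 events the 95% interval would be 0.635 ÷ and × exp(1.96 × √(4/124)), or 0.45 to 0.90.

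**Conclusion.** The point holds in a limited form. The H02 test is valid, but it does not use two baseline measures that every subject has and on which the event itself is defined. The SAP also plans no effect measure or interval, so the size of any delay would not be quantified. This second part needs no assumption about prognostic strength.

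For the first part, the gain is about 5% to 48% more information, or about 3 to 16 points of one-sided power at 214 per arm. It rests on an assumed log-hazard SD of 0.5 to 1.5 and on the planned rates applying at 24 months. Over that range adjusted power stays at about 0.72 or below, so adjustment does not make good the shortfall from 0.80. It should be read as a worthwhile improvement, not as a repair of the sample size.

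**What to change.** Before unblinding, and as a dated change to the SAP:

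- Make the H02 analysis a Cox model, or a discrete-time model suited to the 3-monthly visits, with treatment and continuous baseline fasting glucose and HbA1c. State how ties are handled.
- Report the hazard ratio with an interval whose level is reconciled with the one-sided 0.05 test. A 90% interval matches that test; if 95% is preferred, say how it will be read alongside the test.
- As the quantified answer to goal 1, report the 24-month difference in restricted mean diabetes-free time, or cumulative incidence by arm and its difference, with a 95% confidence interval.
- Keep the log-rank test and the Kaplan-Meier curves as the unadjusted support.

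This needs no new data, visits or subjects, only SAP text and a little programming. The document is dated January 2018 and section 3.6.4 ends the study in April 2018, so a change to the confirmatory analysis must be documented as made blind. The statistical downside is small: the hazard ratio becomes conditional on baseline and assumes proportional hazards.
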